Investigator Studies Program (MISP) Protocol and Procedures	
	Section #1 - MISP Protocol Identification
Study Title:	The title of the protocol should include study design, indication and, where applicable, dosage, dosage form, and comparative agent(s). Single oral dose of azithromycin1 gm with or without amoxicillin2 gm to prevent peripartum infection and sepsis in laboring high-risk women: 3-Arm RCT
Request Date:	11/20/2015; Updated 6/13/2017; 10.1.2017; 11.28.17; 10/20/2018
Institution Name	University of Alabama at Birmingham/Cameroon Health Initiative
Investigator Contact Information: – Full address – Phone No. – Fax No. – e-mail address	[name], MD, PhD Professor, Department of Obstetrics and Gynecology Director, Center for Women's Reproductive Health & Maternal-Fetal Medicine Division [name] [contact] [contact] Email: [contact]

Castion #2. Care Brotocal		
	Section #2- Core Protocol	
2.1 Objectives & Hypotheses	Primary Objective : To test the effectiveness of a single adjunctive oral dose of a) 1g of azithromycin and b) 1g of azithromycin + 2g of amoxicillin, each compared to c) usual care alone (placebo group)in reducing maternal peripartum infections and sepsis in at-risk laboring women in a LIC setting. Hypothesis #1 : A single, oral dose of a) 1g azithromycin or b) 1g azithromycin+2g amoxicillin given for prolonged labor or prolonged membrane rupture in term pregnant women will reduce the risk of peripartum infections and sepsis.	
	Secondary Objectives: 1. To collect and story specimens to estimate the prevalence of mycoplasma and ureaplasma in the genital tract, placenta and chorioamnion and assess whether their presence is associated with peripartum infection in LICs.	
	Hypothesis #2: The presence of genitalureaplasma and mycoplasmas in the placenta and chorioamnion of laboring women will be strongly associated with maternal peripartum infections (similar to our findings in the US).	

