2. Randomization and Drug allocation concealment: Enrolled subjects will be randomly assigned in a 1:1:1 ratio to one of the two prophylactic oral regimens or to no treatment/placebo using either a web-based randomization sequence with varying block sizes and stratified by study site. Alternatively, considering challenges to internet access, a computer-generated randomization scheme with appropriate sequence of use of the interventions will be confidentially maintained in the pharmacy at each site and used to accomplish the random allocation of consecutive patients.

Blinding: As previously discussed we will plan to accomplish blinding with placebo by working with the CBCHS central pharmacy to accomplish identical capsules with and without the active medications. These medications will be packaged according to the predefined sequence into opaque envelopes containing the designated medication. All packages will have capsules that represent azithromycin or placebo and amoxicillin or placebo. The envelopes will be stored in sequential order until a patient is ready for randomization,

3. Medication distribution: The allocated therapy will be provided by the pharmacy staff. Clinical supplies will be received by a designated person at the study site, handled and stored safely and properly, and kept in a secured location for use in study participants as above. Clinical supplies will be dispensed in accordance with the protocol. The pharmacy is responsible for keeping accurate records of the clinical supplies, the amount dispensed for use by the patients, and the disposition at the end of the study.

The allocated therapy will be provided by the pharmacy staff to study staff for distribution.

The patient is considered randomized once the medication is dispensed from the pharmacy and sequential number posted on the patient specific randomization form. The study medication will be initiated immediately (prior to delivery).

On labor anddelivery, achorioamnion swab will be collected by trained research staff into storage tubes with appropriate medium and stored in a dedicated study freezer. Maternal blood will also be collected into the tube provided and frozen as well. Specimens will be shipped to UAB and kept in a biorepository

MISP Protocol and Procedures

I

7

for future testing (shipped in batches as boxes get full). Of note all CBCHS facilities have back-up generators to ensure continuous power.

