	Analyses: Data analyses will follow the CONSORT guidelines. Analyses will be by intention-to-treat in which subjects will be analyzed in the group to which they were randomized, regardless of whether or not they received the assigned intervention. Analyses will be performed at the Center for Women's Reproductive Health, University of Alabama at Birmingham. The key analyses for this study are the comparisons reflected by the primary and secondary aims. The primary analysis will compare the incidence of the composite peripartum infection outcome between each of the active groups and the control groups – a chi-square p-value as well as the relative risk and 95% CI will be computed for each comparisons. The secondary outcomes will be similarly compared. Student's t-test comparisons of continuous outcomes will be done. Standard comparisons of covariate characteristics at baseline between groups will be done. It is anticipated that the randomization scheme will balance the groups for these covariates; however, secondary analyses of relevant outcomes using logistic regression adjustments will be implemented to account for any suggested confounding. A secondary comparison will examine the 2 active groups relative to each other. The data from the ureaplasma/mycoplaema_testing_will_be_similarly_compared_with_the
	 Compared with the baseline colonization rate will be reflected by the findings in the no-treatment/placebe group. Sample Size Calculation, Primary Outcome: This has been previously presented above and is shown here as a reminder. Sample size: Up to15-30% of women who have prolonged labor or membrane rupture will have one or more infections included in the primary endpoint. We assume a baseline risk of 20%. To demonstrate a 50% reduction in peripartum infections in the high-risk group of laboring women (of the same order observed in high risk group who have cesarean) with antibiotic prophylaxis with 80% power and alpha of 0.025 per primary comparison (0.05 total), 241 women per group are needed. Thus 750 women will be needed for the 3 arm

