	comparison. In a sub-study of our US trial 1/3 (30%) of patients had colonization with ureaplasma or mycoplasma. For the cohort of 600, a sample size of 195 will be needed to estimate a prevalence of 25% (±5%) with 95% confidence. Thus, we will have sufficient study population to estimate the prevalence of colonization with ureaplasmas by PCR methods and to assess its role as a risk factor for infection. Testing of the 200 receiving placebo/placebo will provide baseline prevalence whereas the results from the antibiotic exposed groups will allow us to explore whether the prevalence of ureaplasma/mycoplasma colonization is influenced by the exposure between randomization and delivery (when specimens are collected and stored in
2.8 Specific Drug Supply Requirements	appropriate media). The study drugs and identical placebos will be provided with the assistance of the CBCHS Central pharmacy which is responsible for procuring and supplying medications to over 90 CBCHS facilities in Cameroon. Medications will either be purchased through the CBCHS Central Pharmacy or at a certified pharmacy in the US. The CBCHS pharmacy investigator will be responsible for the destruction of the supplies at the study center pursuant to the ICH/GCP Guidelines, local regulations and the investigator's institutional policies. Clinical supplies will be received by a designated person at the study site, handled and stored safely

11

	and properly, and kept in a secured location for use in study participants. Clinical supplies will be dispensed in accordance with the protocol. The pharmacy is responsible for keeping accurate records of the clinical supplies, the amount dispensed for use by the patients, and the disposition at the end of the study.

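### The 195 women for a 25% prevalence ±5 points depend on an undeclared finite-population correction and on a 600-woman trial, while the same section plans 750

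*Combined protocol and SAP*

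**What the plan says.** Section 2.1 sets a secondary objective of collecting "specimens to estimate the prevalence of mycoplasma and ureaplasma in the genital tract, placenta and chorioamnion", and of assessing whether these organisms are associated with peripartum infection in low-income countries.

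Section 2.7 justifies the numbers for that objective: "For the cohort of 600, a sample size of 195 will be needed to estimate a prevalence of 25% (±5%) with 95% confidence". It then concludes that the study population is large enough. For the baseline rate it relies on one arm: "Testing of the 200 receiving placebo/placebo will provide baseline prevalence". The analysis paragraph of section 2.7 says the same, in poorly legible text: the "baseline colonization rate will be reflected by the findings in the no-treatment/placebe group".

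The primary sample-size paragraph, immediately before, requires 241 women per group and rounds up: "Thus 750 women will be needed for the 3 arm" comparison. The randomization section fixes the allocation: "Enrolled subjects will be randomly assigned in a 1:1:1 ratio".

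**The concern.** There are three linked problems.

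- **Unstated assumption.** At the stated prevalence, margin and confidence level, the standard calculation needs about half as many women again as the plan says. The gap closes only with a finite-population correction. That correction suits a description of the enrolled women alone. It does not suit inference to labouring women more widely, which is where the objective in section 2.1 points.
- **Inconsistent inputs.** The prevalence calculation assumes three arms of 200. The primary calculation, a few lines earlier, assumes 750 women.
- **Missing precision.** Baseline prevalence is to come from the placebo arm, but the ±5 points is not stated for that arm. Pooling all arms would be more precise, but study drug is given before delivery and the swab is taken at delivery. Pooling therefore mixes exposed and unexposed women, and section 2.7 itself plans to explore whether that exposure changes colonization.

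At stake is whether a reader can tell what precision the baseline estimate will have, and for which population.

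**Working it through.** **Inputs.** From section 2.7: p = 0.25, d = 0.05, 95% confidence (taken as two-sided, z = 1.96), N = 600, placebo arm 200, trial total 750. From the randomization section: 1:1:1, so 750/3 = 250 per arm. Section 2.7 also cites a colonization rate of about 30% from the investigators' US sub-study.

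**1. Reproducing the plan's figure**

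- No correction: n0 = z²p(1−p)/d² = 1.96² × 0.25 × 0.75 / 0.05² = 288.1, so 289. This is not 195.
- With a finite-population correction at N = 600: n = n0 / (1 + (n0 − 1)/N) = 288.1 / (1 + 287.1/600) = 194.9, so 195. This is an exact match.

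Other methods without the correction also miss: Wilson 286, Clopper-Pearson 306, arcsine about 267 to 306, one-sided z = 1.645 gives 203. An uncorrected calculation at 15% prevalence gives 196, but 15% is not the stated input.

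**2. The same method at the current trial size**

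At N = 750: 288.1 / (1 + 287.1/750) = 208.4, so 209.

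**3. The two trial sizes**

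3 × 200 = 600, whereas 750/3 = 250. Nothing in the text presents the 600 as a subset of the 750. A possible origin is an unadjusted alpha: 20% versus 10% at 80% power needs 199 per arm at two-sided 0.05 (about 600 in total) and 242 at 0.025 (the plan says 241). That explanation is inference, and the conflict does not depend on it.

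**4. Precision actually available**

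Uncorrected half-width = 1.96 × √(p(1−p)/n). The corrected version multiplies this by √((N − n)/(N − 1)).

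| Women tested | p = 25%, uncorrected | p = 30%, uncorrected | p = 25%, corrected |
|---|---|---|---|
| 195 of 600 | ±6.1 | ±6.4 | ±5.0 |
| 200 (placebo, of 600) | ±6.0 | ±6.4 | ±4.9 |
| 250 (placebo, of 750) | ±5.4 | ±5.7 | ±4.4 |
| 600 (all arms) | ±3.5 | ±3.7 | n/a |
| 750 (all arms) | ±3.1 | ±3.3 | n/a |

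If only 90% of 250 placebo specimens were usable (my assumption, n = 225), the uncorrected half-width would be ±5.7 points at 25% and ±6.0 at 30%.

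**The case against.** The best defence is that nothing was miscalculated. The sentence puts N = 600 beside n = 195, which is how a finite-population calculation is often reported, and those inputs return 195 exactly. The conclusion of sufficiency also survives most readings. With the correction, the placebo arm exceeds the requirement at either size (200 against 195, or 250 against 209). Without it, all arms together exceed 289. The ±5 target fails only for the placebo arm alone without the correction, and at 250 women the miss is 0.4 points. Specimens are stored for future testing, and no enrolment number depends on 195.

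Most of this stands, and it limits the size of the problem. It does not remove it:

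- The correction is defensible only if the target is the enrolled cohort. The plan does not say so, and section 2.1 looks to low-income countries.
- The placebo arm is the source the plan itself names for the baseline rate, so the one reading that misses ±5 is not contrived.
- Pooling meets the target for a different quantity, a mixture of exposed and unexposed women.
- The clash between 600/200 and 750 remains on every reading.

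The garbled analysis paragraph is weak evidence by itself, but the sample-size paragraph is clean and names the placebo group. Part of the protocol text was not available here and might explain the 600. It would not reconcile the two adjacent paragraphs as they stand.

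**Conclusion.** The concern holds. The 195 is correct only under a finite-population correction that is not declared and for a trial of 600 that the plan no longer describes. For inference beyond the enrolled women the requirement is 289; for the enrolled cohort of 750 it is 209. The placebo-arm baseline estimate would have a half-width of about ±5.4 points at 25% and ±5.7 at 30% with 250 women, and ±6.0 and ±6.4 with 200, rather than ±5.

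This rests on a two-sided 95% normal-approximation interval, a full set of usable specimens, and 750 as the operative total. The effect is confined to a secondary objective. The primary comparison is untouched provided 750 is the real target; at 200 per arm and alpha 0.025 its power would be 71%, which is a further reason to remove the 600.

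**What to change.** In section 2.7, reconcile the 600/200 with the 750 (about 250 per arm), delete the 195, and state the precision for the group that supplies the baseline rate. For example:

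> If specimens from about 250 placebo/placebo women are tested, the 95% CI half-width for baseline prevalence is about ±5.4 percentage points at 25% and ±5.7 at 30%, without a finite-population correction; fewer usable specimens will widen it.

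If the target is only the enrolled cohort, say so, name the correction, and give the N used (209 needed at N = 750; ±4.4 points from 250 placebo women at 25%). If a pooled figure is also reported, label it as mixing women with and without study antibiotic exposure.

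The cost is wording only. The stated precision for a secondary objective becomes slightly less favourable. No extra women are needed and the primary comparison does not change.

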	Inclusion criteria: Pregnant women with singleton pregnancy in labor at term ≥37 weeks who plan to deliver vaginally and have a) prolonged membrane rupture (≥ 8 hours) or prolonged labor (≥18 hours)* The study is restricted to those at term because those who are preterm may be more likely to receive antibiotics for other reasons and per recommendations. Exclusion criteria: Evidence of chorioamnionitis or other infection requiring antibiotics at time of eligibility, allergy to azithromycin or amoxicillin or any ingredients in the placebo, or plan for cesarean delivery prior to enrollment. Interventions: 1g po Azithromycin/ placebo for amoxicillin, 1g po Azithromycin. Subjects will be stratified by enrollment site.
	develop maternal peripartum infection or death prior to discharge from the hospitalup to 6 weeks postpartum defined as one or more of: a) Chorioamnionitis: Fever (>100.4°F/38°C on two occasions 30 minutes apart or ≥102°F/39°C on one occasion) in addition to one or more of the following: fetal tachycardia >160bpm, maternal tachycardia>100bpm, uterine tenderness or purulent lochia prior to delivery, or diagnosis by a clinician.

1

4

Trained research staff in maternity outcomes reporting at each center (also blinded to study medications) will be responsible for all screening and research data abstraction from patient medical records with the help of clinical investigators and staff. Each hospital will have a designated investigator physician. Research nurses will undergo centralized specific training to screen and ascertain study outcomes. Screening will occur on labor and delivery in the selected CBCHS units and will be conducted by dedicated trained study staff with the assistance of clinical staff. The screening form will be used and completed for each patient screened. Potential subjects will be approached by trained research staff for written consent in English or French. Patients who cannot read will have the consent form read to them. Those that indicate they do not understand will be excluded. Study subjects will be randomized only after eligibility criteria have been confirmed and the patient has consented to participate by signing the informed consent form. The randomization form will be used to complete randomization

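### Colonization is swabbed at delivery but assessed as a risk factor for an infection outcome that includes chorioamnionitis, so for those events the exposure is measured after the outcome

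*Combined protocol and SAP*

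**What the plan says.** Hypothesis #2 in section 2.1 reads: "The presence of genitalureaplasma and mycoplasmas in the placenta and chorioamnion of laboring women will be strongly associated with maternal peripartum infections". Section 2.7 goes further and says the study population will be large enough to estimate colonization prevalence by PCR and "to assess its role as a risk factor for infection".

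Section 2.7 also fixes when the exposure is measured. It will explore whether colonization is "influenced by the exposure between randomization and delivery (when specimens are collected and stored in" suitable media. The procedures text (item 3, medication distribution) describes a chorioamnion swab taken on labor and delivery. The readable text describes no specimen taken before randomization.

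On the outcome side, the end of section 2.2 lists sepsis, chorioamnionitis, endometritis, other wound infection and death. Item a) of the primary outcome definition requires, for chorioamnionitis, fever plus one or more of fetal tachycardia, maternal tachycardia, "uterine tenderness or purulent lochia prior to delivery, or diagnosis by a clinician". The exclusion criteria remove women with "Evidence of chorioamnionitis or other infection requiring antibiotics at time of eligibility".

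**The concern.** A risk-factor analysis needs the exposure to be recorded before the outcome, or at least to be unaffected by it. That holds here for endometritis, wound infection and sepsis arising postpartum. It does not hold for chorioamnionitis. Women who have it at eligibility are excluded, so counted cases arise between enrollment and delivery, ahead of the swab.

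The infection itself, or antibiotics given for it, may then alter what the swab detects. Pooling all infections mixes a correctly ordered association with one measured in reverse order. The pooled estimate could hide a real association or create a false one, and it would not support calling colonization a risk factor.

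Section 2.7 recognizes that study drug may change colonization before the swab and uses the placebo group for baseline prevalence. That does not address this problem. A woman on placebo who develops chorioamnionitis is also swabbed after her outcome, so neither restriction to placebo nor adjustment for arm removes it.

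**Working it through.** **The plan's own figure.** Section 2.7 gives 195 women to estimate a prevalence of 25% ± 5% with 95% confidence in a cohort of 600. Without correction, n₀ = 1.96² × 0.25 × 0.75 / 0.05² = 288.1. With the finite population correction, 288.1 / (1 + 287.1/600) = 194.9, so 195 reproduces. It is a precision size for prevalence. It says nothing about power for the association with infection, or about time order.

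**Time order by component.**

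| Component | Onset relative to the swab |
|---|---|
| Chorioamnionitis | Before (fetal tachycardia and the pre-delivery signs are intrapartum) |
| Sepsis | Before or after |
| Endometritis, wound infection | After |

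**Possible distortion (illustration).** From section 2.7: 20% baseline risk, about 30% colonized (the US sub-study figure), 200 placebo women. Assumed: the true relative risk (RR), the chorioamnionitis share of events, and the effect on detection.

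For true RR 2.0, risk in the uncolonized is 0.20 / (0.70 + 0.30 × 2) = 0.1538, and in the colonized 0.3077. The cells are:
- colonized (60 women): 18.46 infected, 41.54 not;
- uncolonized (140 women): 21.54 infected, 118.46 not.

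*Loss of detection.* Chorioamnionitis is 50% of events and half of its colonized cases test negative. Move 18.46 × 0.5 × 0.5 = 4.62 women to the uncolonized group. Observed RR = (13.85/55.38) / (26.15/144.62) = 0.250/0.181 = 1.38.

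*Gain in positivity.* Chorioamnionitis is 50% of events and a quarter of its uncolonized cases test positive. Move 21.54 × 0.5 × 0.25 = 2.69 women the other way. Observed RR = (21.15/62.69) / (18.85/137.31) = 0.337/0.137 = 2.46.

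Repeating this across shares:

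| Chorioamnionitis share of events | 25% | 50% | 75% |
|---|---|---|---|
| True RR 2.0, half of colonized cases lost | 1.67 | 1.38 | 1.12 |
| True RR 2.0, a quarter of uncolonized cases gained | 2.22 | 2.46 | 2.73 |
| True RR 1.0, half of colonized cases lost | 0.86 | 0.73 | 0.60 |
| True RR 1.0, a quarter of uncolonized cases gained | 1.17 | 1.36 | 1.57 |

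If detection is unaffected, the RR does not change, but the order of measurement is still reversed. These RRs do not depend on whether the placebo arm has 200 women (colonization text) or 250 (750/3 from the sample-size text).

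**Precision cost of separating the outcomes.** Of 200 × 20% = 40 placebo events, 30, 20 or 10 remain as postpartum infections if chorioamnionitis is 25%, 50% or 75%. The power check is a two-sided 0.05 comparison of 60 colonized with 140 uncolonized women, with pooled variance under the null. For all events, the standard error is 0.0617 under the null and 0.0669 under the alternative, so z = (0.1538 − 1.96 × 0.0617) / 0.0669 = 0.49 and power is about 69%. The same calculation with overall risks of 15%, 10% and 5% gives 55%, 40% and 24%. With 250 placebo women, power is 77.7% for all events, falling to 63.5%, 46.4% and 27.4%.

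**The case against.** The strongest reply is that the aim is modest. Section 2.1 speaks of association, specimens are stored for future testing, and a cross-sectional association would satisfy that wording. Colonization may also predate the swab biologically, so only the order of measurement is reversed. Both points stand. They confine the problem to the risk-factor claim in section 2.7 and do not remove it.

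The public text is also incomplete. The sentence in 2.7 on comparing the ureaplasma/mycoplasma data is broken, and the outcome list is readable only through item a). A restriction to postpartum outcomes, or an earlier specimen, may be stated in text that cannot be read.

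A reader might infer more than the documents support:
- *Antibiotics before the swab affect only cases, so the bias is toward no association.* Section 2.2 describes usual care as including prophylaxis after 18 hours of membrane rupture, so non-cases may be exposed too. The same section says antibiotics are not given solely for these risk factors; the two statements must be reconciled. Treatment of intrapartum chorioamnionitis is itself inferred from the exclusion wording, and loss of PCR detection is not documented. Infection could also raise positivity.
- *Chorioamnionitis is before delivery by definition.* The timing phrase may attach only to the local signs, and the clinician-diagnosis route carries no timing. Essentially intrapartum is as far as the text goes.
- *The US work being mirrored had the swab before the outcome.* The documents do not give its swab timing.
- *Only postpartum infections in women without chorioamnionitis should be analyzed.* That conditions on a possible consequence of colonization and loses many events, so it suits a sensitivity analysis better.

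**Conclusion.** The point holds for a secondary aim. As the readable text stands, colonization measured at delivery will be assessed as a risk factor for infection with no split by onset, and for chorioamnionitis (and any sepsis beginning before delivery) the measurement follows the outcome. This conclusion rests on the timing statements alone and needs no assumption about treatment.

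The direction and size of any bias are unknown. The illustrated range, 1.12 to 2.73 for a true relative risk of 2.0 and 0.60 to 1.57 for no true association, shows only that distortion either way is possible and grows with the chorioamnionitis share. That share and both detection effects are assumptions. The randomized comparison of infection rates is untouched.

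**What to change.** In section 2.7, alongside any all-infection association, report the colonization association separately for:

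(a) infections with onset after delivery: endometritis, wound infection and postpartum sepsis;
(b) chorioamnionitis, labelled as a cross-sectional association.

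Use the term risk factor only for (a), and association otherwise. Assign sepsis by its onset relative to delivery. As a sensitivity analysis, repeat (a) without women who had chorioamnionitis, stating that this conditions on a possible consequence of colonization. Flag antibiotics given before the swab wherever the forms record them.

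Most of this is wording. The readable text does not show whether the forms capture infection onset and antibiotic timing; if they do not, the sepsis assignment and the antibiotic flag would need added fields or must be declared unavailable. The statistical cost is fewer events and a wider interval for (a), which the plan should acknowledge.

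### Colonization is swabbed after study drug, and section 2.7 does not say that its association with infection (Hypothesis #2) will be stratified by or adjusted for arm

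*Combined protocol and SAP*

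**What the plan says.** Hypothesis #2 (section 2.1) is that ureaplasma and mycoplasma in the placenta and chorioamnion of laboring women "will be strongly associated with maternal peripartum infections". It is not restricted to any arm.

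The study procedures have the medication started straight after randomization and before delivery, and a chorioamnion swab collected on labor and delivery. The sample-size text in section 2.7 confirms the order: results from the antibiotic-exposed groups will be used to explore whether "colonization is influenced by the exposure between randomization and delivery".

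The same text gives the size calculation, "For the cohort of 600, a sample size of 195 will be needed", for a prevalence of 25% ± 5%. It then concludes that the study population is sufficient both to estimate prevalence and "to assess its role as a risk factor for infection". The 200 placebo women are named as the source of baseline prevalence. No model, population or arm term follows for the association.

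The general analysis paragraph of section 2.7 specifies a chi-square test and an RR with 95% CI, with secondary outcomes compared in the same way. It then provides for logistic regression to deal with suggested confounding, directly after discussing baseline covariates that randomization should balance.

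**The concern.** Colonization here is a post-randomization variable. Both active arms contain azithromycin, which section 2.2 describes as covering genital ureaplasmas and mycoplasmas, and section 2.7 assumes treatment halves infection. If drug also reduces colonization by delivery, arm becomes a common cause of both variables. Placebo women would be over-represented among the colonized and would also have the higher infection risk.

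A crude colonized-versus-not comparison across all arms would then show excess infection in colonized women even if the organisms played no part in any arm. The error runs in the direction Hypothesis #2 predicts, so it could be read as confirmation. Nothing in the plan prevents that analysis from being run as the main one.

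Separately, the claim that the population is sufficient for the risk-factor aim rests on a calculation that does not address an association.

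**Working it through.** **The plan's own figures.**

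- Prevalence: n0 = 1.96² × 0.25 × 0.75 / 0.05² = 288.1. With a finite population correction for 600, n = 288.1 / (1 + 287.1/600) = 194.9, so 195 reproduces. It is the precision of one proportion and contains no RR and no power.
- Primary comparison, 20% versus 10%, two-sided 0.025, 80% power: [z(0.9875)·√(2 × 0.15 × 0.85) + z(0.80)·√(0.16 + 0.09)]² / 0.10² = 241.1, against 241 stated.

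**Inputs for the check.** Infection is 20% on placebo and 10% on active drug (section 2.7). There are 250 per arm (750 in total) or 200 per arm (the 600/200 used in the colonization text); section 2.7 contains both. Placebo colonization is taken as 30%, the US sub-study figure quoted in section 2.7; applying it in this setting is an assumption. Active-arm colonization is not given anywhere, so it is varied, with the same value in both active arms. Within every arm, colonization and infection are independent (true RR 1).

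**Expected crude RR**, example with 15% colonization on active drug and 250 per arm:

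- Colonized: 75 placebo + 75 active = 150; infected 15 + 7.5 = 22.5, or 15.0%.
- Not colonized: 175 placebo + 425 active = 600; infected 35 + 42.5 = 77.5, or 12.9%.
- Crude RR = 15.0/12.9 = 1.16.

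**All scenarios.** Rejection rates are at two-sided 0.05, from 100,000 simulated trials each.

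| Active-arm colonization | Crude RR | Crude false positives, 250/arm | Crude false positives, 200/arm | Stratified by arm (Mantel-Haenszel test) |
|---|---|---|---|---|
| 30% (unchanged) | 1.00 | 5.1% | 5.1% | 5.0% |
| 20% | 1.10 | 7.7% | 7.1% | 4.9–5.0% |
| 15% | 1.16 | 11.3% | 10.3% | 5.0–5.1% |
| 10% | 1.25 | 17.5% | 15.5% | 5.0% |
| 5% | 1.38 | 27.7% | 23.9% | 4.9–5.0% |

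**Ceiling.** If drug cleared colonization entirely, the colonized group would be 75 placebo women with 15 infections (20.0%). The rest would be 675 women with 35 + 50 = 85 infections (12.6%), giving RR 1.59.

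**Sensitivity.** With 25% placebo colonization, halving it on active drug gives a crude RR of 1.15 instead of 1.16.

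**Power for a true RR of 2** (two-sided 0.05).

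- Placebo arm alone: risk in the non-colonized is 0.20 / (0.3 × 2 + 0.7) = 15.4%, and 30.8% in the colonized. With 60 versus 140 women, the null SE is √[0.16 × (1/60 + 1/140)] = 0.0617 and the alternative SE is 0.0669. Power = Φ[(0.1538 − 1.96 × 0.0617)/0.0669] = Φ(0.49) = 69%. With 75 versus 175 women it is 78%. At RR 2.5 the figures are 90% and 95%.
- All arms, stratified by arm, simulated with active-arm colonization from 5% to 30%: 78% to 91% with 200 per arm, and 86% to 96% with 250 per arm.

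**The case against.** The strongest reply is that the plan leaves this analysis unspecified and does not specify a wrong one. A reader might infer that section 2.7 prescribes a pooled, unadjusted, whole-cohort comparison. The documents do not support that. The risk-factor sentence states a purpose only, and the sentence on how the ureaplasma/mycoplasma data will be compared is incomplete in the text available, so no weight can be put on it. The 600 is the finite population in the prevalence calculation and is not declared as the analysis set. Naming the placebo women for baseline prevalence does not exclude using them for the association. The logistic-regression clause could be stretched to admit an arm term.

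A reader might also infer that the plan expects drug to change colonization. It says only that this will be explored, and without such a change there is no bias.

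Finally, the stakes are limited. This is a secondary hypothesis on stored specimens, the primary comparison is untouched, and arm is recorded for everyone, so it can be added at analysis.

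All of that stands as a limit on the claim, but it does not remove it. The adjustment clause follows a sentence about baseline covariates, and arm is not one of them. The only method the section sets out for comparisons is the crude one. For an exposure measured after randomized treatment, silence about arm leaves the biased analysis available as the default.

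**Conclusion.** The point holds as a gap in specification with a conditional, modest bias. The order of dosing and swabbing, the spectrum of azithromycin and the assumed halving of infection all come from the documents. The fall in colonization does not, and the size of the bias depends on it. If active-arm colonization falls from 30% to between 20% and 5%, a crude pooled analysis gives RR 1.10 to 1.38 with no true association. The false-positive rate is about 8% to 28% with 250 per arm, or 7% to 24% with 200. If colonization is unchanged, the RR is 1.00 and the rate 5%.

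It would go too far to say that treatment alone could manufacture the strong association that Hypothesis #2 predicts. Under the plan's infection rates the crude RR cannot exceed about 1.6 at 30% placebo colonization, and the upper figures in the range need a very large fall before delivery. The realistic risk is a nominally significant result, or an inflated estimate, taken as support.

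That 195 does not justify sufficiency for the risk-factor aim holds regardless of any drug effect on colonization.

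**What to change.** In section 2.7:

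1. Make the main Hypothesis #2 estimate arm-stratified: a Mantel-Haenszel RR over the three arms, or a model with an arm term, with a check of the arm-by-colonization interaction.
2. Report the placebo arm alone beside it, since that is the only arm in which the swab reflects colonization without study drug.
3. Label any crude pooled estimate as descriptive.
4. Replace the bare claim of sufficiency for the risk-factor aim with a detectable RR, for example the power at RR 2 and 2.5 shown above. State whether 600 or 750 women apply, because the section uses both.

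The cost is wording only, with no new samples or participants. The statistical price is some precision. Stratified power at RR 2 is about 78% to 96%, depending on arm size and remaining colonization, and the placebo arm alone has 69% to 78%. Where drug lowers colonization, part of the crude analysis's apparent power is the bias itself, so it is not a fair benchmark.
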